PROTOCOL TITLE: Hypoglycemia after exercise in type 1 diabetes: Intranasal naloxone as a novel therapy to preserve hypoglycemia counterregulation

VERSION 8 – December 7, 2018

ABBREVIATIONS/DEFINITIONS

- DSMB: Data and Safety Monitoring Board
- DSMP: Data and Safety Monitoring Plan
- Euglycemia: normal blood glucose concentration (60-100 mg/dL)
- Hypoglycemia: low blood glucose (<60 mg/dL)

PROTOCOL TITLE: Hypoglycemia after exercise in type 1 diabetes: Intranasal naloxone as a novel therapy to preserve hypoglycemia counterregulation

VERSION 8 – December 7, 2018

STUDY SUMMARY

Study Title	Hypoglycemia after exercise in type 1 diabetes: Intranasal naloxone as a novel therapy to preserve hypoglycemia counterregulation
Study Design	Randomized, placebo-controlled, crossover design
Primary Objective	Determine if intranasal administration of naloxone during exercise will be a novel approach to preserve the counterregulatory response to hypoglycemia experienced the next day in individuals with type 1 diabetes
Secondary Objective(s)	Pharmacokinetics and pharmacodynamics of naloxone using a population modeling design to explore dosing for future studies
Research Intervention(s)/ Investigational Agents	Naloxone
IND/IDE #	134687 (exempt)
Study Population	Individuals with Type 1 diabetes
Sample Size (number of participants)	Approximately 30
Study Duration for Individual Participants	Up to 15 weeks

1.0 Objectives

1.1 Purpose:

The overall objective of this project is to determine if the intranasal administration of naloxone during exercise will be a novel approach to preserve the counterregulatory response to hypoglycemia experienced the next day in patients with type 1 diabetes. Exercise induced autonomic failure contributes to the development of impaired awareness of hypoglycemia. Treatments that blunt the consequences of exercise induced autonomic failure, such as preserving the post-exercise counterregulatory response to hypoglycemia, may improve awareness of hypoglycemia. Naloxone, an opioid antagonist, is an extremely promising agent. In healthy volunteers, intravenous administration of naloxone during exercise preserved the counterregulatory response to hypoglycemia the following day (1). In this study, we will extend the clinical applicability by administering intranasal naloxone to individuals with type 1 diabetes. Specifically, we will use a randomized, placebo controlled, crossover design to administer drug or placebo to patients with type 1 diabetes during acute exercise and assess the counterregulatory response to hypoglycemia the following day. The use of intranasal naloxone is a highly innovative aspect of this proposal. Intranasal naloxone translates readily to clinical use and, as demonstrated by our preliminary data, achieves similar plasma drug concentrations as after IV administration.

The specific aims and the hypotheses they address are:

Aim 1: To assess the impact of intranasal naloxone administered during exercise on Day 1 on hypoglycemia induced symptom scores measured on Day 2.

Hypothesis 1: Compared to placebo, intranasal naloxone administered on Day 1 will result in higher symptom scores in response to hypoglycemia on Day 2.

Aim 2: To assess the impact of intranasal naloxone administered during exercise on Day 1 on hypoglycemia induced epinephrine secretion on Day 2.

Hypothesis 2: Compared to placebo, intranasal naloxone administered on Day 1 will result in higher peak epinephrine levels in response to hypoglycemia on Day 2.

Secondary aims include assessment of the tolerability of the treatment and evaluation of the effect of the intervention on glycemic control as measured by continuous glucose monitoring for 7 days after each treatment. In addition, the pharmacokinetics of intranasal naloxone will be characterized and the relationship between plasma drug concentration and response will also be explored. In this proof of principle experiment, we will determine if the administration of intranasal naloxone preserves the counterregulatory response to subsequent hypoglycemia. If it does, future investigation will focus on developing this agent for use in the real world, with experiments designed to identify the minimum dose necessary to achieve the preservation, define the duration of the effect, and examine the ease of usability for patients with type 1 diabetes.

2.0 Background

2.1 Significance of Research Question/Purpose:

Glycemic management and quality of life of patients with type 1 diabetes are adversely impacted by hypoglycemia and its associated fear. Because patients with type 1 diabetes are unable to reduce endogenous insulin secretion and increase glucagon secretion when blood

PROTOCOL TITLE: Hypoglycemia after exercise in type 1 diabetes: Intranasal naloxone as a novel therapy to preserve hypoglycemia counterregulation

VERSION 8 – December 7, 2018

glucose falls they become critically dependent on the sympathoadrenal response to a fall in glucose to prevent profound hypoglycemia. Unfortunately, the sympathoadrenal response is easily blunted by everyday life experiences such as exercise, as has been shown in both healthy controls (2) and participants with type 1 diabetes (3), leading to impaired awareness of subsequent hypoglycemia. Up to 25% of patients with type 1 diabetes are estimated to have impaired awareness of hypoglycemia (4, 5), which places them at great risk for severe hypoglycemia and potential death. Prevention of impaired awareness of hypoglycemia and reversal of the condition when it occurs requires meticulous avoidance of hypoglycemia, which is nearly impossible in this patient group that experiences one or more episodes of hypoglycemia each week (6).

In particular, there is a critical need to address impaired awareness of hypoglycemia induced by exercise. In exercise induced autonomic failure, the glucose level that triggers the counterregulatory response to hypoglycemia on a day after exercise is lower than the value that triggers the response to hypoglycemia on a day following inactivity. Indeed, the first sign of hypoglycemia in the days following exercise may be neuroglycopenia (7). Many practitioners instruct patients with type 1 diabetes to reduce insulin doses in anticipation of hypoglycemia during and after exercise, but such measures have not been beneficial in reducing hypoglycemia that occurs many hours post activity (8). Therefore, innovative therapies that preserve the counterregulatory response to hypoglycemia experienced post exercise are urgently needed.

2.2 Preliminary Data:

In healthy volunteers, intravenous administration of naloxone during exercise preserved the counterregulatory response to hypoglycemia the following day (1).

2.3 Existing Literature:

Activation of opioid signaling in the brain is believed to be one mechanism that contributes to the development of impaired awareness of hypoglycemia (8). Previous studies have demonstrated that intravenous administration of the opioid antagonist naloxone during exercise prevents the development of exercise associated autonomic failure in humans (1).

Intranasal administration has long been used for therapies like glucocorticoids and has recently become available as an emergency treatment for opioid drug overdose using naloxone, the same drug we will test in this trial. Easy to use and highly portable, a intranasal delivery device that can be used during exercise to administer a drug already shown to prevent exercise induced autonomic failure would greatly expand the options available to patients with type 1 diabetes who want to exercise without putting themselves at risk for impaired awareness of hypoglycemia in subsequent days.

3.0 Study Endpoints/Events/Outcomes

3.1 Primary Endpoint/Event/Outcome:

The primary outcome variable for Aim 1 will be the difference, naloxone vs. saline, in symptom scores collected using a standard questionnaire during the hypoglycemic clamp on Day 2, after administration of intranasal treatment during exercise on Day 1.

The primary outcome variable for Aim 2 will be the difference, naloxone vs. saline, in peak epinephrine levels measured during the hypoglycemic clamp on Day 2, after administration of treatment during exercise on Day 1.

3.2 Secondary Endpoint(s)/Event(s)/Outcome(s):

Secondary endpoints will include:

- Glucose levels will be measured by continuous glucose monitor and home blood glucose monitoring during the 7 days after each experiment with specific levels of interest of > 54 mg/dL, > 54 mg/dL - < 70 mg/dL, and ≤ 70 mg/dL.
 - Percentage of time of specific ranges
 - Total count of specific ranges
 - Total hypoglycemia symptoms counted during specific ranges
- Plasma naloxone concentrations will be collected to model the pharmacokinetics and pharmacodynamics using a population modeling approach. This will be used to investigate dose levels and regimens for future studies.

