5.0 Procedures Involved

5.1 Study Design:

This is a single center, single-blind randomized cross over design trial that will compare the impact of intranasal naloxone vs. intranasal saline administration during exercise on day 1 on the response to hypoglycemia on day 2.

Figure 1. Study Design

5.2 Study Procedures:

Screening Visit: At the screening visit, informed consent will be obtained; a standardized form will be used to insure participants meet inclusion/exclusion criteria, and baseline hemoglobin A1c will be collected. Clinical A1c from the medical record can be used if within one month of screening.

Following the collection of blood samples, participants will have their peak aerobic capacity (VO_2 peak) determined. Participants will be fitted with a neoprene breathing mask that is connected to an open-circuit spirometry metabolic cart for the collection of expired gas samples. After a warm-up on an electronically-braked bicycle ergometer for 5 minutes, participants will complete a progressive resistance exercise test until volitional exhaustion. VO_2 peak will be measured using methodology and equipment already established by our group (9). This measurement will then be used to determine the exercise workload necessary to achieve 60% of VO_2 peak during the intervention phases of the study, as was done by Milman (1).

-6 days Part 1 Day 1: In preparation for the intervention visits, participants will be instructed to avoid hypoglycemia in the week before day 1 since that may blunt their response to hypoglycemia during the protocol. They will be asked to avoid exercise, to wear a continuous glucose monitor (provided by the study) during the 6 days before the exercise study and the one day after, and to

PROTOCOL TITLE: Hypoglycemia after exercise in type 1 diabetes: Intranasal naloxone as a novel therapy to preserve hypoglycemia counterregulation

VERSION 8 – December 7, 2018

monitor and record their blood sugars before meals, at bedtime, and any time they have symptoms of hypoglycemia. Participants will also be given instructions for diabetes management during the days before the study to safely ensure at home insulin has cleared the body by the start of the study.

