Participants will be instructed to call the investigators if they have symptomatic hypoglycemia with a glucose of <70 mg/dL or asymptomatic hypoglycemia with a glucose of <54 mg/dL during the 6 days before the exercise studies, after discharge on day 1 or before the hypoglycemic clamp is started on day 2. Participants will be rescheduled if they have episodes of hypoglycemia (defined as symptomatic hypoglycemia and a blood glucose or CGM reading <70 mg/dL or asymptomatic hypoglycemia with a blood glucose of < 54 mg/dL) for more than 20 minutes in the days before Day 1 of the study.

Part 1 Day 1: Participants will be instructed to report for the visit in a fasting state. Before any other research procedures take place, participants will be randomized to receive either naloxone or saline. Intravenous catheters will be placed for the subsequent infusion of 1.0 mU/kg/min insulin, potassium phosphate or potassium chloride (120 mEq/l at 40 cc/hr), and 20% dextrose as needed to maintain euglycemia. When participants reach euglycemia (~ 95 mg/dL), they will be instructed to begin exercise on a stationary bicycle. Adjustments in the exercise workload will be made to assure that participants exercise at a workload requiring 60% of their VO₂peak for 45 minutes based on the VO₂ measured every 15 minutes. They will then be given a 5 minute rest break, followed by another 45 minute period of exercise at 60% VO₂peak. At the start of exercise and 45 minutes after the start of the morning exercise period, participants will be given a 4.0 mg doses of intranasal naloxone or saline in the same volume, according to the randomization assignment.

Participants may be asked to allow a download of their personal glucose meter/pump data. This will be done in research offices using secure software specific for the brand of the glucose meter/pump.

At the completion of the morning exercise, participants will be allowed to rest 3 hours and eat a 15g carbohydrate measured snack. Glycemia will be maintained at euglycemia during this rest period.

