Participants will be contacted at 1 week post final study procedure for adverse event assessment. This can be done by either telephone or email.

PROTOCOL TITLE: Hypoglycemia after exercise in type 1 diabetes: Intranasal naloxone as a novel therapy to preserve hypoglycemia counterregulation

VERSION 8 – December 7, 2018

	Screening	-6 to -1 days Part 1 Day 1	Part 1 Day 1		Part 1 Day 2	+1 to +7 days Part 1 Day 2	7 Week Washout Period	CGM-Only -7 Days before Part 2	-6 to -1 days Part 2 Day 1	Part 2 Day 1		Part 2 Day 2	+1 to +7 days Part 2 Day 2
			AM	PM						AM	PM		
Consent	X												
A1c	X										X		
VO ₂ peak/bike	X												
Education	X												
Urine Pregnancy Test	X		X								X		
Apply CGM	X								X				
Wear CGM		X	X	X	X	X				X	X	X	X
Home blood sugar monitoring		X				X				X			X
Randomization			X										
Download glucose meter/pump			X								X		
Exercise			X	X							X	X	
IV Infusion (insulin, glucose, potassium)			X	X	X						X	X	X
Naloxone/saline			X ¹	X ¹							X ¹	X ¹	
Blood collection: naloxone concentrations (only collected during active study drug)			X ²	X ²							X ²	X ²	
Blood collection: hormones (epinephrine, norepinephrine, glucagon, cortisol)					X ⁶								X ⁶
Glucose measurement			X ⁵	X ⁵	X ⁵						X ⁵	X ⁵	X ⁵
Blood Pressure	X												
Heart Rate			X ³	X ³							X ³	X ³	
VO ₂			X ⁴	X ⁴							X ⁴	X ⁴	
Questionnaires	X				X ⁷								X ⁷
Usual Activities							X						
Snack, if necessary			X	X	X						X	X	X
Meal				X	X						X	X	

¹ Naloxone/saline 4.0mg administered twice, time zero and +30 minutes

² Serum collection for naloxone at time points every 20-40 minutes

³ Heart rate collected continuously

⁴ VO₂ collected every 15 minutes

⁵ Collected from IV, resulted on bedside Analox machine

⁶ Serum collection: hormones

⁷ Questionnaires every 15 minutes

PROTOCOL TITLE: Hypoglycemia after exercise in type 1 diabetes: Intranasal naloxone as a novel therapy to preserve hypoglycemia counterregulation

VERSION 8 – December 7, 2018

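### As printed, the first glucose level in the CGM and home-glucose secondary endpoint (> 54 mg/dL) is not a low-glucose level, and no listed level isolates readings of 54 or below

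*Combined protocol and SAP*

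**What the plan says.** Section 3.2 sets CGM and home glucose measurements over the 7 days after each experiment as a secondary endpoint, "with specific levels of interest of > 54 mg/dL, > 54 mg/dL - < 70 mg/dL, and ≤ 70 mg/dL". Three summaries are then attached to those levels: "Percentage of time of specific ranges", "Total count of specific ranges" and "Total hypoglycemia symptoms counted during specific ranges". The aim behind them, in section 1.1, is "evaluation of the effect of the intervention on glycemic control as measured by continuous glucose monitoring for 7 days after each treatment".

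Two other places bear on how the levels should read:

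- The definitions at the front of the protocol put hypoglycemia below 60 mg/dL and euglycemia at 60 to 100 mg/dL.
- Section 5.2 asks participants to call the investigators for "symptomatic hypoglycemia with a glucose of <70 mg/dL or asymptomatic hypoglycemia with a glucose of <54 mg/dL". The rescheduling rule that follows uses the same two cut-points in the same direction. Section 5.2 is not stated to be the source of the endpoint levels.

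No other section restates or corrects the list. Section 16.1 says only that secondary outcomes are handled in the same way as the primary ones, with a model suited to the scale.

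**The concern.** The third summary counts hypoglycemia symptoms within each level, so one expects levels that separate degrees of low glucose. The first printed level does not do this. It is open-ended upward, and it excludes exactly the readings (54 or below) that a cut-point of 54 would normally be there to pick out.

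An analyst who programs the list literally would produce a first-level count and symptom count that do not describe low glucose, and no count at 54 or below. An analyst who silently repairs it has more than one repair to choose from, and the choice would be unrecorded.

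**Working it through.** The plan gives no figure to reproduce, so the check is one of set membership, followed by what each summary loses.

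**Step 1. Place each glucose value in the printed levels.** The inputs are the three levels in section 3.2.

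| Glucose (mg/dL) | First: > 54 | Second: > 54 to < 70 | Third: ≤ 70 |
|---|---|---|---|
| 54 or below | no | no | yes |
| above 54, below 70 | yes | yes | yes |
| exactly 70 | yes | no | yes |
| above 70 | yes | no | no |

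The first level contains the second entirely, together with the protocol's whole euglycemic range (60 to 100) and everything higher. Under the protocol's own definition of hypoglycemia, only its part below 60 is low. Values of 54 or below fall in the third level alone. The third level minus the second leaves 54 or below plus exactly 70, so the low range is not isolated by subtraction either.

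**Step 2. Percent time.** Let L be the percent of time at 54 or below. Then percent time > 54 = 100 − L. If L falls from 1.0 to 0.5 (assumed values), the first level rises from 99.0 to 99.5. The change is 0.5 points either way, with opposite sign. In a linear mixed model of the kind in section 16.1, replacing L by 100 − L reverses the sign of the treatment estimate and leaves its standard error and p-value unchanged.

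**Step 3. Counts.** Section 3.2 does not say whether the count is of readings or of episodes. Suppose it is of readings, taken evenly in time as on a CGM. The documents give no time shares, so these are assumptions: L as above, M the percent strictly between 54 and 70, E the percent at exactly 70. The share of the first level lying above 70 is (100 − L − M − E) / (100 − L).

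- L = 1, M = 3, E = 0.2: 95.8 / 99 = 96.8%
- L = 0.5, M = 2, E = 0.1: 97.4 / 99.5 = 97.9%
- L = 5, M = 6, E = 0.4: 88.6 / 95 = 93.3%

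The third level minus the second gives L + E: 1.2 against a true 1, 0.6 against 0.5, and 5.4 against 5. Without an overall total, which section 3.2 does not list, the count at 54 or below is therefore known only up to the readings at exactly 70. With a total, it is the total minus the first level.

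These shares should not be carried over to home meter readings. The row "Home blood sugar monitoring" is marked in the schedule for both follow-up weeks, but the reading times ("monitor and record their blood sugars before meals, at bedtime, and any time they have symptoms of hypoglycemia") are stated only for the days before Day 1. They include symptom-triggered readings, which would not be spread evenly over the glucose range.

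**Step 4. Symptom counts.** On the first level these would include symptoms logged at any normal or high glucose and omit every symptom logged at 54 or below. The documents give no basis for saying how many symptoms would fall in each range.

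**Step 5. Which repair?** Two sets fit the context.

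- *Only the first sign is reversed:* ≤ 54, > 54 to < 70, and a cumulative ≤ 70. Exactly 70 then sits only in the cumulative level.
- *The first and third signs are reversed:* ≤ 54, > 54 to < 70, and ≥ 70. Every value falls in exactly one level.

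If the lowest level is written as < 54, exactly 54 falls only in the cumulative level under the first set and in no level under the second. Nothing in the documents decides between these.

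**The case against.** The text was read from PDF, and the point turns on inequality signs. That the same line also shows < and ≤ proves that those symbols can be read, not that each one was read correctly. This stands: the finding concerns the text as printed, and the sponsor's source must be checked.

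The levels are called levels of interest, the aim is glycemic control in general, and overlapping levels are not in themselves an error. That is fair as far as it goes. It does not explain counting hypoglycemia symptoms over a range that is mostly normal and high glucose, or having no level for the lowest readings when section 5.2 treats 54 as an upper limit of low glucose.

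A reader might infer that the endpoint has lost information or power. The documents do not support that. Percent time is an exact complement, the reading count at 54 or below is recoverable except for values at exactly 70 (and fully so if totals are reported), and every level can be recomputed from the recorded values.

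A reader might also infer that the second and third levels are sound and only the first is wrong. That is not established either. One of the two plausible repairs changes the third sign as well.

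**Conclusion.** Wrong as written, and minor. It is an inconsistency in an endpoint definition, not a miscalculated figure. As printed, the first level is not a low-glucose level and no level isolates 54 or below; both statements follow from the list alone and need no assumption.

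The practical effect is confined to one secondary endpoint. Percent time is affected only in direction. The first-level reading count would mostly reflect normal and high glucose: above 70 for 93.3% to 97.9% of it under the assumed time shares, and only if the count is of evenly spaced readings. The symptom count on that level would be taken over the wrong range. Primary outcomes, sample size and safety rules are unaffected.

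That a sign was reversed is an inference from section 5.2 and the protocol's definitions. Which set was intended cannot be told from the documents.

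**What to change.** Before treatment comparisons are seen, the sponsor should:

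- check all the inequality signs in section 3.2 against the source;
- correct the list so that the lowest range, written as ≤ 54 or < 54, has its own level;
- state where exactly 54 and exactly 70 fall;
- state whether the third level is a cumulative low range or a band that is not low;
- apply the same levels to percent time, counts and symptom counts.

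Either set in step 5 would serve statistically once it is recorded. The call and rescheduling rules in section 5.2 are not part of this change. The cost is one line of endpoint wording. No new data are needed, because the levels can be recomputed from the glucose values already recorded.

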4.0 Study Intervention(s)/Investigational Agent(s)

4.1 Description:

This is a single center, single-blind randomized cross over design trial that will compare the impact of intranasal naloxone vs. intranasal saline administration during exercise on day 1 on the response to hypoglycemia on day 2.

Our investigational product is Narcan® intranasal spray, manufactured by ADAPT Pharma, which contains 4 mg naloxone in each metered dose. Naloxone is an opioid antagonist and is FDA approved as both intravenous and intranasal formulations for the complete or partial reversal of opioid depression, including respiratory depression, induced by natural and synthetic opioids.

4.2 Drug/Device Handling:

Investigational Drug Services will handle all drug requirements including randomization and blinding, dispensing, and storage.

4.3 IND/IDE:

[figure not shown]
Exempt IND #134687

